5.2.2 Exclusion Criteria

1. Use of any herbal supplements (including milk thistle) within 2 weeks or 10 half-lives (if known) of the respective supplement, whichever is longer, prior to the first dosing of study drug.

2. Females who are pregnant or plan to become pregnant, or breastfeeding, or males whose partners are pregnant or planning to become pregnant within 7 months (or per local RBV label) after their last dose of study drug.
3. Recent (within 6 months prior to study drug administration) history of drug or alcohol abuse that could preclude adherence to the protocol.
4. Positive test result for Hepatitis B surface antigen (HbsAg) or anti HIV Ab positive.
5. HCV genotype performed during screening indicates co infection with any genotype other than genotype 3.
6. Use of known strong inducers of cytochrome P450 3A (CYP3A) or any strong inducers of P-glycoprotein (e.g., phenobarbital, rifampin, carbamazepine, St. John's Wort) and any medications listed below, as well as those that are contraindicated for SOF, ritonavir or RBV, if applicable, within 2 weeks prior or 10 half-lives of the medication whichever is longer, to study drug administration including but not limited to:

Table 3. Medications Contraindicated for Use with the Study Drug Regimen

Alfuzosin	Ergot Derivatives	Quinidine
Alprazolam	Estazolam	Rifabutin
Amiodarone	Estrogen-containing medications for systemic use	Rifampin
Ampiroxicam	Flecainide	Rifapentine
Astemizole	Flurazepam	Rivaroxaban
Azelnidipine	Fusidic Acid	Salmeterol
Bepridil	Lovastatin	Sildenafil*
Blonanserin	Midazolam	Simvastatin
Carbamazepine	Oxcarbazepine	St. John's Wort
Cisapride	Phenobarbital	Tadalafil
Clorazepate	Phenytoin	Terfenadine
Diazepam	Pimozide	Triazolam
Efavirenz	Piroxicam	Vardenafil
Eletriptan	Propafenone	Voriconazole

* When used for the treatment of pulmonary arterial hypertension.

Note: Not all medications contraindicated with SOF, ritonavir and ribavirin are listed above. Refer to the most current package inserts or product labeling of ritonavir and ribavirin for a complete list of contraindicated medications.

7. Clinically significant abnormalities or co-morbidities, other than HCV infection that make the subject an unsuitable candidate for this study in the opinion of the investigator.
8. History of uncontrolled seizures, uncontrolled diabetes as defined by a glycated hemoglobin (hemoglobin A1C) level > 8.5% at the Screening Visit, active or suspected malignancy or history of malignancy (other than basal cell skin cancer or cervical carcinoma in situ) in the past 5 years.
9. Any cause of liver disease other than chronic HCV infection, including but not limited to the following:
 - Hemochromatosis
 - Alpha-1 antitrypsin deficiency

- Wilson's disease
- Autoimmune hepatitis
- Alcoholic liver disease
- Drug-related liver disease

10. Receipt of any investigational product within a time period equal to 10 half-lives of the product, if known, or a minimum of 6 weeks prior to study drug administration.

11. Consideration by the investigator, for any reason, that the subject is an unsuitable candidate to receive ombitasvir, ABT-450, ritonavir, SOF, or RBV (if applicable).

12. Current enrollment in another clinical study, previous enrollment in this study, or previous use of any investigational or commercially available anti-HCV therapy (other than interferon, pegIFN, RBV, and/or SOF) including previous exposure to telaprevir, boceprevir, ABT-450, or ombitasvir (ABT-267). Subjects who previously participated in trials of investigational anti-HCV agents may be enrolled with the approval of the AbbVie Study Designated Physician if they can produce documentation that they received only placebo. Concurrent participation in a non-interventional, epidemiologic, or registry trial may be permitted with approval by the AbbVie Study Designated Physician.

13. Uncontrolled clinically significant cardiac, respiratory (except mild asthma), hepatic (except HCV-related disease), gastrointestinal, hematologic, or psychiatric disease or disorder, or any uncontrolled medical illness, which is unrelated to the hepatic disease.

14. History of solid organ transplant.

15. Any current or past clinical evidence of cirrhosis such as ascites or esophageal varices, or prior biopsy showing cirrhosis, e.g., a Metavir score > 3 or an Ishak score > 4 .

16. Screening laboratory analyses showing any of the following abnormal laboratory results:

- Calculated creatinine clearance (using Cockcroft-Gault method) < 30 mL/min.

- Albumin < Lower limit of normal (LLN).
- Prothrombin time/International normalized ratio (INR) > 1.5. Subjects with a known inherited blood disorder and INR > 1.5 may be enrolled with permission of the AbbVie Study Designated Physician.
- Hemoglobin < LLN.
- Platelets < 120,000 cells per mm³.
- Absolute neutrophil count (ANC) < 1500 cells/µL (< 1200 cells/µL for subjects of African descent who are black).
- Indirect bilirubin > 1.5 × ULN and direct bilirubin > ULN.

Rationale for Exclusion Criteria

1, 3, 5, 10, 12	To avoid bias for the evaluation of efficacy and safety by concomitant use of other medication
2, 6 – 8, 11, 13 – 16	To ensure safety of the subjects throughout the study
4, 9	To exclude subjects with liver diseases other than HCV

5.2.3 Prior and Concomitant Therapy

Any medication or vaccine (including over-the-counter or prescription medicines, vitamins and/or herbal supplements) that the subject is receiving at the time of enrollment, or receives during the study, must be recorded along with the reason for use, date(s) of administration including start and end dates, and dosage information including dose, route and frequency. The Investigator should review all concomitant medications for any potential interactions.

During the PT Period, all medications will be recorded until 30 days following the last dose of study drugs. Only medications associated with HCV treatment will be collected thereafter.

The AbbVie Study Designated Physician should be contacted if there are any questions regarding concomitant or prior therapy(ies).

5.2.3.1 Prior HCV Therapy

Subjects may have previously received prior interferon, pegIFN, RBV, and/or SOF treatment and failed treatment (either on treatment or via relapse post-treatment). All available documentation of prior treatment history, including start and stop dates and HCV RNA levels, should be collected in the source to document the type of non-response.

Subjects must have discontinued prior therapy at least 2 months prior to the Screening Visit in order to be eligible for the study.

Prior or current use of any other investigational or commercially available anti-HCV agents other than interferon, pegIFN, RBV, and/or SOF, excludes a subject from this study. Subjects who previously participated in trials of investigational anti-HCV agents may be enrolled if they can provide documentation that they received only placebo.

5.2.3.2 Concomitant Therapy

Subjects must be able to safely discontinue any prohibited medications or herbal supplements within 2 weeks or within 10 half-lives of the respective medication/supplement (if known), whichever is longer, prior to initial study drug administration and through 2 weeks following discontinuation of study drugs. Subjects must be consented prior to discontinuing any prohibited medications or herbal supplements for the purpose of meeting study inclusion criteria.

The investigator should confirm that concomitant medication can be safely administered with DAAs (including ritonavir) and RBV, if applicable. Some medications may require dose adjustments due to potential for drug-drug interactions. Subjects should be on a stable dose of concomitant medications for at least 2 weeks prior to initiation of study drug. The investigator can also review the label(s) for the concomitant medication(s) for additional information.

During the PT Period, investigators should reassess concomitant medications and subjects may resume previously prohibited medications, or revert to pre-study doses, 2 weeks following discontinuation of study drugs, if applicable.

Influenza vaccinations and all essential vaccinations in this subject population are allowed during Screening through the PT Period.

5.2.3.3 Prohibited Therapy

Subjects must be able to safely discontinue any prohibited medications within 2 weeks or within 10 half-lives of the respective medication/supplement (if known), whichever is longer, prior to initial study drug administration through 2 weeks following discontinuation of study drugs. Subjects must be consented prior to discontinuing any prohibited medications for the purpose of meeting study inclusion criteria.

In addition to the medications listed in [Table 3](#), use of known strong inducers of CYP3A or strong inhibitors or inducers of P-glycoprotein is prohibited within 2 weeks of the respective medication/supplement prior to the initial dose of study drug through the first 2 weeks after the subject has completed study drugs.

Refer to the current local labels for ritonavir, RBV, and SOF for a list of prohibited medications. Anti-HCV medications other than those specified in the protocol will not be allowed during the treatment period of the study.

Contraceptives

Prior to enrollment, subjects should agree to practice two effective methods of birth control while receiving study drugs starting with Study Day 1 and for 7 months after stopping study drug or as directed by the local ribavirin label. Subjects using systemic estrogen-containing contraceptive therapy (including estrogen-containing oral contraceptives) have a higher risk for elevated ALT levels. Subjects using these medications must discontinue them at least 2 weeks prior to study drug administration or 10 half-lives (if known), whichever is longer. Subjects may replace the systemic

estrogen-containing contraceptive with a progestin-only hormonal contraceptive method. Estrogen-containing contraceptives may be resumed 2 weeks after the last dose of DAAs.

Use of hematopoietic growth factors is not permitted during this study without the approval of the AbbVie Study Designated Physician. Management of hematologic growth factor therapy is the responsibility of the investigator; growth factors will not be provided by AbbVie, and AbbVie will not reimburse for the expense of growth factors or their use.

Investigators should refer to the package inserts for erythropoiesis stimulating agents for additional information regarding their use.

5.3 Efficacy Pharmacokinetic, Pharmacogenetic and Safety Assessments/Variables

5.3.1 Efficacy and Safety Measurements Assessed and Flow Chart

Study procedures described in this protocol are summarized in [Table 4](#) and [Table 5](#).

Table 4. Study Activities – Treatment Period

Activity	Screening ^a	Day 1/ Baseline ^b	Wk 1	Wk 2	Wk 4	Wk 8	Wk 10	Wk 12 (EOT)	Premature D/C Treatment ^c
Informed Consent	X								
Provide RBV Medication Guide ^d	X								
Medical History	X	X ^e							
Physical Exam	X	X						X	X
Vital Signs, Weight, Height ^f	X	X	X	X	X	X	X	X	X
ECG ^g	X						X	X	X
Hematology/Chemistry/Urinalysis/Coagulation Panel	X	X	X	X	X	X	X	X	X
Pregnancy Test (serum [s] urine [u]) ^h	X (s)	X (u, s)			X (u)	X (u)	X (u)	X (u)	X (u)
FSH (all females)	X								
HBsAg, Anti-HCV Ab, Anti HIV Ab	X								
HgbA1c	X								
HCV Genotype and Subtype	X								
Liver Biopsy or FibroTest or FibroScan [®]	X								
IL28B Sample	X								
Pharmacogenetic Sample (Optional)		X							
Messenger RNA (mRNA) Sample (Optional)		X		X			X	X	
Total Insulin		X					X	X	X

Table 4. Study Activities – Treatment Period (Continued)

Activity	Screening ^a	Day 1/ Baseline ^b	Wk 1	Wk 2	Wk 4	Wk 8	Wk 10	Wk 12 (EOT)	Premature D/C Treatment ^c
Concomitant Medication Assessment	X	X	X	X	X	X	X	X	X
Adverse Event Assessment	X ^k	X	X	X	X	X	X	X	X
Patient Report Outcomes Instruments (PROs) ^j		X		X	X	X	X	X	X
Study Drugs Dispensed		X		X	X	X	X	X	
Study Drugs Collected and Compliance Reconciled in IRT					X	X	X	X	X
HCV RNA Samples	X	X	X	X	X	X	X	X	X
HCV Resistance Sample		X	X	X	X	X	X	X	X
Archive Plasma Sample	X	X	X	X	X	X	X	X	X
Archive Serum Sample	X	X	X	X	X	X	X	X	X
Pharmacokinetic Samples ^m		X	X	X	X	X	X	X	X
Interferon Gamma-Induced Protein 10 (IP-10) Sample		X		X	X	X	X	X	X

EOT = End of treatment; D/C = Discontinuation

- a. A signed study-specific informed consent will be obtained from the subject (with proper source documentation reflecting this process) before any study procedures are performed at the Screening Visit.
- b. All procedures will be performed prior to first dose.
- c. All subjects should begin PT Period after the subject prematurely discontinues study drugs treatment in this period.
- d. Where applicable/locally available.
- e. The medical history will be updated at the Day 1 Visit. This updated medical history will serve as the Baseline for clinical assessment.
- f. Height will be measured at the Screening Visit only.

Table 4. Study Activities – Treatment Period (Continued)

- g. Evaluate the Screening ECG prior to dosing to determine eligibility.
- h. Urine pregnancy test is not required after the Day 1 Visit for female subjects with a documented history of bilateral tubal ligation, bilateral oophorectomy or hysterectomy or who are confirmed to be post-menopausal. A positive urine pregnancy test requires a confirmatory serum test.
- i. For subjects who have not had a qualifying liver biopsy within the previous 24 months.
- j. If the optional pharmacogenetic sample is not collected at Study Day 1, it may be collected at any other visit during the study. Verify subject has given consent to pharmacogenetic testing.
- k. Protocol-related nonserious adverse events will be collected from the time the subject signed the study-specific informed consent until study drug administration.
- l. EuroQol 5 Dimensions 5 Levels Health State Instrument (EQ-5D-5L) and Fatigue Severity Scale (FSS) should be administered before any study procedures and in the order listed.
- m. PK samples will be collected at 2, 4, and 6 hours post-DAA dose at Day 1. Additional intensive PK samples will be collected at the Week 2 study visit where samples will be collected at pre-dose and approximately 2, 4, and 6 hours post-DAA dose. On the day of intensive blood sampling, subjects will take their morning dose of DAs and ribavirin onsite in the presence of study site personnel and the time of administration will be recorded to the nearest minute.

Table 5. Study Activities – Post-Treatment (PT) Period

Activity	PT Wk 2	PT Wk 4	PT Wk 8	PT Wk 12	PT Wk 24	PT Wk 36	PT Wk 48 or PT D/C
Vital Signs and Weight	X	X	X	X	X	X	X
Hematology/Chemistry/Urinalysis/Coagulation Panel		X		X			
Monthly Pregnancy Test (females) ^a		X	X				(Weeks 12, 16, 20, 24, 28)
PRO Instruments ^b		X	X	X	X	X	X
Concomitant Medication Assessment ^c	X	X	X	X	X	X	X
Adverse Event Assessment ^d	X	X	X				
HCV RNA Samples	X	X	X	X	X	X	X
HCV Resistance Sample	X	X	X	X	X	X	X
Archive Plasma Sample	X	X	X	X	X	X	X
Archive Serum Sample	X	X	X	X	X	X	X
IP-10 Sample					X		X
mRNA Sample (Optional)		X			X		

Wk = Week; PT D/C = Post-Treatment Discontinuation

a. Urine pregnancy testing is not required after the Day 1 Visit for female subjects with a documented history of bilateral tubal ligation, hysterectomy, bilateral oophorectomy, or who are confirmed post-menopausal. For subjects on a RBV-inclusive regimen, subjects may have an unscheduled office visit for pregnancy testing or elect to perform the tests at home with test kits provided by the site at PT Weeks 16, 20 and 28. Additional testing may be required per local RBV label.

b. EuroQol5 Dimensions 5 Levels Health State Instrument (EQ-5D-5L) and Fatigue Severity Scale (FSS) should be administered before any study procedures and in the order listed.

Table 5. Study Activities – Post-Treatment (PT) Period (Continued)

- c. Only medications related to the treatment of HCV will be collected after 30 days post-dosing.
- d. Adverse events and serious adverse events will be collected until 30 days post-dosing.

Note: Day 1 of the PT Period will be defined as the day after the last dose of active study drug treatment.

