8.1.3 Patient Reported Outcomes

The following exploratory analyses of patient reported outcomes (PROs) will be performed:

- mean change from baseline in EQ-5D-5L health index score and its VAS score to each applicable post-baseline time point
- mean change from baseline in the FSS score and its VAFS score to each applicable post-baseline time point

Summary statistics (n, mean, SD, median, minimum and maximum) at each visit and for change from baseline to each visit will be provided for the EQ-5D-5L health index and its VAS scores, and the FSS and its VAFS scores.

Additional analyses of PROs will be performed as useful and appropriate.

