6.2 Analysis Windows

For efficacy analyses of HCV RNA and resistance, the time windows specified in [Table 2](#), [Table 3](#), [Table 4](#), and [Table 5](#) describe how efficacy data are assigned to protocol-specified time points during the Treatment and PT Periods, respectively. All time points and corresponding time windows are defined based on the blood sample collection date.

For visit windows of analyses of health-related quality of life (QoL) patient reported outcomes (PROs) collected throughout the study, [Table 6](#) will be used.

For laboratory data and vital signs, the time windows specified in [Table 2](#), [Table 3](#), [Table 4](#), and [Table 7](#) describe how data are assigned to protocol specified time points during the Treatment and PT Periods.

If more than one assessment is included in a time window, the assessment closest to the nominal time will be used. If there are two observations equally distant to the nominal time, the latest one will be used in analyses. The only exception to this is for the SVR windows (e.g., SVR₄, SVR₁₂, and SVR₂₄); for these windows, the last value in the window will be used.

If multiple measurements are made on the same day for a safety laboratory parameter or a vital sign parameter, the average of the values will be used in analyses. For summaries of shifts from baseline and potentially significant values, multiple values on the same day will not be averaged; all values will be considered for these analyses.

Table 2. Analysis Time Windows for HCV RNA, Resistance Endpoints, Laboratory Data, and Vital Sign (Treatment Period) for 12-Week of Treatment

Scheduled Visit	Nominal Day (Study Day)	Time Window (Study Day Range)
Day 1/Baseline ^a	1 ^a	≤ 1 ^a
Week 1	7	2 to 10
Week 2	14	11 to 21
Week 4	28	22 to 42
Week 8	56	43 to 63
Week 10	70	64 to 77
Week 12	84	78 to 98
Final Treatment Visit ^b		2 to ≤ 2 days after last dose of study drug

a. Day of first dose of study drug.

b. The last value within the window will be used to define the Final Treatment visit value. The upper bound of this Final window is Study Drug End Day ≤ 2.

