Note: The result closest to the scheduled time point will be used, except for SVR₄, SVR₁₂, and SVR₂₄. Data must also have Study Drug End Day > 2 for all windows. Study Drug End Day 0 is defined as the day of the last dose of study drug.

Table 6. Analysis Time Windows for PRO Instruments

Scheduled Visit	Nominal Day (Study Day)	Time Window (Study Days Range)
12-Week Treatment		
Day 1/Baseline	1 ^a	≤ 1 ^a
Week 4	28	2 to 42
Week 8	56	43 to 70
Week 12	84	71 to 98
Final Treatment Visit ^b		2 to ≤ 2 days after last dose of study drug
8-Week Treatment		
Day 1/Baseline	1 ^a	≤ 1 ^a
Week 4	28	2 to 42
Week 8	56	43 to 70
Final Treatment Visit ^b		2 to ≤ 2 days after last dose of study drug
6-Week Treatment		
Day 1/Baseline	1 ^a	≤ 1 ^a
Week 4	28	2 to 35
Week 6	42	36 to 49
Final Treatment Visit ^b		2 to ≤ 2 days after last dose of study drug
Scheduled Visit	Nominal Day (Study Drug End Day)	Time Window (Study Drug End Days Range)
Post-Treatment Week 4	28	3 to 56
Post-Treatment Week 12	84	57 to 126
Post-Treatment Week 24	168	127 to 252
Post-Treatment Week 48	336	253 to 378
Final Post-Treatment Visit ^c		> 2 days after last dose of study drug

- a. Day of first dose of study drug.
- b. The last value within the window will be used to define the Final Treatment visit value. The upper bound of this Final window is Study Drug End Day ≤ 2.
- c. The last value within the Post-Treatment Period window will be used to define the Final Post-Treatment visit value. The lower bound of this Final window is Study Drug End Day 3.

Note: The result closest to the scheduled time point will be used. For visits during treatment, data must also be within 2 days of the last dose of study drug. For post-treatment visits, data must also have Study Drug End Day > 2 where Study Drug End Day 0 is defined as the day of the last dose of study drug.

Table 7. Laboratory Data and Vital Sign Visit Windows (Post-Treatment Period)

Scheduled Time	Nominal Day (Study Drug End Day)	Time Window (Study Drug End Days Range)
Post-Treatment Week 2	14	3 to 21
Post-Treatment Week 4	28	22 to 42
Post-Treatment Week 8	56	43 to 77
Post-Treatment Week 12	84	78 to 126
Post-Treatment Week 24	168	127 to 210
Post-Treatment Week 36	252	211 to 294
Post-Treatment Week 48	336	295 to 999
Final Post-Treatment Visit ^a		> 2 days after last dose of study drug

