10.8 Patient Reported Outcomes

The following instruments will be used to collect patient reported outcomes (PROs): EuroQol 5 Dimensions 5 Levels Health State Instrument (EQ-5D-5L) and Fatigue Severity Scale (FSS). Missing data for each measurement will be handled as described in Section 6.3.

The following exploratory analyses of PROs will be performed:

- mean change from baseline in EQ-5D-5L health index score and its VAS score to each applicable post-baseline time point;
- mean change from baseline in the FSS score and its VAFS score to each applicable post-baseline time point.

Subject's responses to the EQ-5D-5L will be combined into a unique health state using a 5-digit code with 1 digit from each of the 5 dimensions. The EQ-5D-5L states will be converted into a single preference-weighted health utility index score by applying country-specific weights (if available) or US weights (if not available). The VAS score will be measured separately.

The FSS measures the impact of fatigue over the past week on specific types of functioning. The survey consists of 9 questions using a 7-point Likert scale. A total score

is calculated as the average of the individual item responses (adding up all the answers and dividing by nine). Subjects also rate their perception of their fatigue on a separate visual analogue fatigue scale (VAFS). Higher FSS scores indicate a higher degree of impact of fatigue.

Summary statistics (n, mean, SD, median, minimum and maximum) for the mean change from baseline to each applicable visit will be provided for the EQ-5D-5L index and its VAS scores, the FSS score and its VAFS scores.

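### The printed protocol collects PROs at Weeks 2 and 10 and Post-Treatment Weeks 8 and 36, but SAP Table 6 has no window for these 4 of 11 post-baseline visits

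*Protocol*

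**What the plan says.** **Schedule.** Protocol Section 5.3.1 sets out when the EQ-5D-5L and FSS are completed.

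- Table 4, row "Patient Report Outcomes Instruments (PROs": Day 1, Weeks 2, 4, 8, 10 and 12, and the premature discontinuation visit.
- Table 5, row "PRO Instruments": PT Weeks 4, 8, 12, 24, 36 and 48 (the last shared with PT discontinuation).

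**Promised analysis.** Protocol Section 8.1.3 plans "mean change from baseline in EQ-5D-5L health index score and its VAS score to each applicable post-baseline time point", with the same for the fatigue scale, and summary statistics at each visit. SAP Section 10.8 repeats this, for example "mean change from baseline in the FSS score and its VAFS score to each applicable post-baseline time point". Both documents call the analyses exploratory.

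**Windows.** SAP Section 6.2 assigns the PRO data to one table: "For visit windows of analyses of health-related quality of life (QoL) patient reported outcomes (PROs) collected throughout the study" are taken from Table 6, "Analysis Time Windows for PRO Instruments". For 12-week treatment its rows are Week 4 (Days 2–42), Week 8 (43–70) and Week 12 (71–98). The post-treatment rows are PT Week 4 (end days 3–56), PT Week 12 (57–126), PT Week 24 (127–252) and PT Week 48 (253–378). Final Treatment and Final Post-Treatment rows are added.

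**Selection rule.** "If more than one assessment is included in a time window, the assessment closest to the nominal time will be used"; ties go to the later value. For the Final Treatment row, "The last value within the window will be used to define the Final Treatment visit value".

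**The concern.** The protocol and the SAP do not describe the same set of PRO visits. A questionnaire completed at Week 2, Week 10, PT Week 8 or PT Week 36 has to fall into a window belonging to another visit. There it is either passed over in favour of that visit's own score or, if that score is missing, presented as though it had been collected at that visit.

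What is at stake is how faithfully fatigue and health state over time are described. With about 10 subjects per randomised arm, one substituted score carries about 1/10 of the weight in a visit mean. Subjects also complete questionnaires at four visits for which the plan has no by-visit summary.

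**Working it through.** The plan gives no figure to reproduce. The check maps each scheduled PRO day onto SAP Table 6.

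**Inputs.** Scheduled visits come from Protocol Tables 4 and 5. Nominal days are 7 × week, as in SAP Tables 2 and 5. Window limits come from SAP Table 6, 12-week and post-treatment rows.

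**Count.** Post-baseline scheduled visits: 5 on treatment + 6 post-treatment = 11, not counting the discontinuation visits. Visits with their own Table 6 row: 3 + 4 = 7. Without one: 11 − 7 = 4, and 4/11 = 36% (2 of 5 on treatment, 2 of 6 post-treatment).

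**Where the four visits fall.**

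| Visit | Nominal day | Table 6 window on that day | Distance from that window's nominal day | One day later |
|---|---|---|---|---|
| Week 2 | 14 | Week 4 (2–42) | 28 − 14 = 14 days | Week 4, 13 days |
| Week 10 | 70 | Week 8 (43–70) | 70 − 56 = 14 days | Week 12, 84 − 71 = 13 days |
| PT Week 8 | 56 | PT Week 4 (3–56) | 56 − 28 = 28 days | PT Week 12, 84 − 57 = 27 days |
| PT Week 36 | 252 | PT Week 24 (127–252) | 252 − 168 = 84 days | PT Week 48, 336 − 253 = 83 days |

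On its nominal day, PT Week 36 is 84 days from PT Week 24 and also 336 − 252 = 84 days from PT Week 48. Three of the four visits fall on the last day of a window, so a one-day delay changes which visit they can stand in for.

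**Selection rule applied.** If the visit that owns the window was completed on schedule, its distance from nominal is 0 and the extra score is not used in the by-visit table. If that visit is missing, the extra score is the only one in the window and takes its label. A subject who stops soon after Week 2, for example, contributes that score to the Week 4 row.

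**Comparison with other data.** SAP Table 2 has separate rows for Week 2 (11–21) and Week 10 (64–77). SAP Tables 5 and 7 have separate rows for PT Week 8 (43–77) and PT Week 36 (211–294). Only the PRO table lacks them.

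**The case against.** **The visit marks may be misread.** The argument rests on the positions of X marks in two tables read from PDF, and there are signs of trouble. The PRO row in Table 4 carries footnote letter j, which is the pharmacogenetic note; the PRO note is l. The dispensing row shows the same six visits, including Week 12 at end of treatment. Yet sofosbuvir comes in 28-tablet bottles, taken one a day and supplied in exact amounts, which fits Day 1, Week 4 and Week 8 better. Table 5 marks adverse event assessment at PT Week 8, although its footnote ends collection at 30 days. No text outside the two grids confirms PROs at the four visits.

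This lowers confidence but does not remove the conflict. The pharmacokinetic row in Table 4 gives 3 + 1 + 4 + 1 + 1 + 1 + 1 = 12 samples, matching the roughly 12 in Protocol Section 5.3.2.1, so the Week 10 column is real. The laboratory and vital-sign rows of Table 5 agree with the note under SAP Table 7. Neither check tests the PRO row itself.

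**The versions differ.** The protocol supplied covers two arms and about 20 subjects; the SAP covers Arms A to F and about 70. A later protocol may have changed the PRO schedule. SAP Section 12.1 names only resistance changes from the latest protocol, which could mean that Table 6 matches a schedule not supplied here. Still, Arms A and B are the arms this protocol describes, and neither document shows a PRO change.

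**Table 6 is coherent in itself.** Its cut-points are midpoints for a schedule without the four visits: (28 + 56)/2 = 42, (56 + 84)/2 = 70, and post-treatment 56, 126 and 252. The edge positions therefore follow from how the windows were built and are not separate evidence of error. This stands.

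**The SAP may choose which exploratory visits to tabulate.** It may, but it does not say that it has. Both documents refer to each applicable time point.

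**Conclusion.** As printed, the PRO schedule and SAP Table 6 conflict at 4 of 11 post-baseline visits for the 12-week regimen and its follow-up. This should be reconciled before the PRO tables are programmed. The conclusion assumes that the X marks were read correctly and that the supplied schedule still applies to Arms A and B. If only the Week 2 and Week 10 marks proved wrong, PT Weeks 8 and 36 would still lack windows.

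Three stronger readings are not supported:

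- A reader might infer that these questionnaires are discarded. They are not lost in every case: a score from any of these visits can be the Final Treatment or Final Post-Treatment value, and Protocol Section 8.1.3 allows further PRO analyses. Relabelling arises only when the neighbouring visit is missing.
- A reader might infer that the randomised ribavirin comparison is compromised. No between-arm PRO comparison is planned; the summaries are descriptive and exploratory. SVR12 and the other efficacy and safety results are unaffected.
- A reader might extend the on-treatment finding to the 8- and 6-week arms. The documents give no PRO schedule for those arms, so nothing can be said about their on-treatment rows.

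**What to change.** 1. Check the PRO marks in the original Protocol Tables 4 and 5 and in the protocol version governing each arm.
2. For each confirmed visit, add a row to SAP Table 6 for the 12-week arms and the post-treatment period. Use the cut-points of SAP Tables 2 and 5, and merge the Week 1 and PT Week 2 windows, where no PRO is scheduled, into the next visit. If all four visits are confirmed:
   - On treatment: Week 2 (2–21), Week 4 (22–42), Week 8 (43–63), Week 10 (64–77), Week 12 (78–98).
   - Post-treatment: PT Week 4 (3–42), PT Week 8 (43–77), PT Week 12 (78–126), PT Week 24 (127–210), PT Week 36 (211–294), PT Week 48 (295–378).
   - The limits for Week 2 and PT Week 4 are merged: Table 2 has 2–10 and 11–21, and Table 5 has 3–21 and 22–42.
3. Change the 8- and 6-week on-treatment rows only if those arms' schedule includes PRO visits without a window.
4. If the sponsor prefers not to tabulate these visits, the SAP should say so and state whether their scores may stand in for a neighbouring visit.

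Cost: a SAP wording change and up to four more rows in exploratory tables, with no new data. Neighbouring visits will have slightly more missing cells, because scores from other visits no longer fill them.
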